Efficacy assessment: a major unsolved question. Unlike after prostatectomy, where PSA levels fall to zero soon after successful surgery, after local targeted therapy (HDR) PSA levels are poor measures of efficacy. PSA falls to a variable nadir due to continued production by residual prostate tissue as well as potential occult non-index tumor that was outside the boost region. Even the Phoenix criterion for radiation failures (2 ng/ml rise above nadir), now a *de facto* standard, has a sensitivity and specificity of only ~65% and ~77%, respectively, for clinical recurrence [71]. False negatives may occur early because it takes time for tumor to grow back fast enough to generate 2 ng/ml of PSA. False positives may be due to residual BPH, regeneration of normal prostate tissue, and prostatitis. PSA is especially problematic for ablation because some portions of the gland are left entirely untreated. The potential for residual under-treated target tumor, or occult non-target tumor to progress, and potentially become clinically significant, highlights the unmet need for sensitive surveillance methods after local targeted therapy.

Therapeutic options after local treatment. Evidence from salvage treatment for post-prostatectomy recurrence reveals that success is more likely when treatment is initiated early [72]. One theoretical advantage of local treatments is that tissue damage is restricted to the prostate. This enables options for local retreatment and second line therapy after failure. After brachytherapy, local recurrence can potentially be retreated with more brachytherapy. This ability to retreat further highlights the need for sensitive surveillance methods after initial treatment.

Can mpMRI also help find recurrence or residual tumor *after* local targeted therapy? It is much more difficult to interpret mrMRI after treatment [73]. For example, after radiation therapy, decreased exocrine function, and fibrosis can cause low signal on T2-weighted images and variable diffusion restriction that mimic tumor [74]. Similarly, after ablation, resolving hemorrhage and proteinaceous necrosis can cause variable diffusion restriction, and inflammation can cause contrast enhancement [75].

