Because there may be multiple lesions per-patient and an indefinite number of non-lesions, the primary analysis will be per-region. Each of the 12 regions will have gold-standard positive or negative information, as well as imaging positive or negative assessments. Predictive accuracy of PI-RADS composite score (mpMRI) and SUV_{\max} PET uptake values will be assessed by ROC analysis using univariable logistic regression for the presence of PC. Areas under the entire ROC curve, and partial area at fixed 90% specificity will be compared. Additional benefit of the other modalities over mpMRI alone will be tested by a multivariable logistic regression. All analyses will be adjusted for clustering within patient.

Statistical Power and Sample Size: Based on our clinical experience at Stanford, we expect an average of 2 PC-positive regions and 10 PC-negative regions per patient. Assuming mpMRI has sensitivity of 80% and specificity of 80-90% [91], a sample size of 1200 regions with 20% prevalence will provide 90% power at 5% error to demonstrate non-inferiority of a PET sensitivity of 90% at 80-90% specificity [62, 92, 93].

The per-lesion analysis will depend on the number of lesions found but will be similar. We will also explore whether specific imaging findings are especially accurate in detection of specific subtypes of PC or prostate regions (i.e., peripheral versus transitional zones). It may also be the case that

predictive failures in imaging may be associated with a particular subtype. Given the small sample, we acknowledge that this analysis will be exploratory.

10.2 Aim 2

Participants: Those enrolled in Aim 1.

Design: Patients will be scanned with both ⁶⁸Ga-RM2 PET/MRI and ⁶⁸Ga-PSMA-11 PET/MRI at six months after initiation of therapy. MRI and PET images will each be evaluated separately.

Outcome measures: Changes in MRI features and/or changes in radiopharmaceutical uptake in lesions will be recorded for each modality in each patient. Gold standard of response to treatment and of PFS will be based on standard clinical follow-up (PSA, imaging, tissue diagnosis including IHC stains for GRPr and PSMA)

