Test to be evaluated: All T1w, T2w, DWI and DCE MR images will first be analyzed and graded by two-board certified abdominal radiologists with subspecialty training in body MRI and extensive clinical experience in prostate MRI (Drs. [name] and [name]), before and after treatment. Areas of focally increased ⁶⁸Ga-RM2 or ⁶⁸Ga-PSMA-11 uptake above surrounding background on pre-therapy scans will be evaluated for changes in uptake by Drs. [name] and [name].

Hypotheses

Primary: Change in ⁶⁸Ga-RM2 or ⁶⁸Ga-PSMA-11 uptake from baseline (T0) to 6 months after start of treatment (T1) will predict treatment response better than T0-T1 changes in MRI.

Secondary: T0-T1 change in ⁶⁸Ga-RM2 or ⁶⁸Ga-PSMA-11 uptake will predict progression-free survival (PFS) better than MRI.

Statistical Analysis:

Primary: (a) logistic regression of response/non-response at T6 on T1-T0 change in PET/MRI measures; (b) McNemar tests of MRI and PET predictions of T6 response.

Secondary: (a) log-rank tests of PFS time (length of drug response) on patients dichotomized as above/below the median change in PET/MRI measures; (b) Cox proportional-hazards regressions of PFS on amount of T1-T0 change in PET/MRI measures.

Statistical Power and Sample Size: We expect a 70-80% response rate to treatment, and 20% of responders progressing by two years.

A sample size of ~75 responders and ~25 non-responders will provide 90% power at one-sided 5% error to detect sensitivity low as 80% at fixed 90% specificity, and to demonstrate a difference in sensitivities of 10 percentage points (e.g., 80% vs 90%).

Median-change groups of ~40 each among the responders will provide 90% power at one-sided 5% error to detect differences in PFS hazard ratios as small as 2.5.

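### Both primary Aim 2 analyses use response at T6, which the plan never defines; if T6 means month 6, it coincides with the T1 scan and nothing is predicted

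*Combined protocol and SAP*

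**What the plan says.** Section 10.2 places the repeat scans "at six months after initiation of therapy". Its primary hypothesis is that the change in tracer "uptake from baseline (T0) to 6 months after start of treatment (T1) will predict treatment response better than T0-T1 changes in MRI". Two primary analyses follow: (a) "logistic regression of response/non-response at T6 on T1-T0 change in PET/MRI measures" and (b) "McNemar tests of MRI and PET predictions of T6 response".

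On how response is judged, section 10.2 says only: "Gold standard of response to treatment and of PFS will be based on standard clinical follow-up". It then lists PSA, imaging and tissue diagnosis in brackets. It gives no response criteria, no assessment date and no rule for cases where the components disagree.

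The power paragraph adds: "We expect a 70-80% response rate to treatment, and 20% of responders progressing by two years".

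Section 2.1, in its discussion of efficacy assessment, states that "after local targeted therapy (HDR) PSA levels are poor measures of efficacy", and that false negatives may arise early because regrowth takes time to raise PSA by 2 ng/ml.

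Section 2.5 and the footnote to the section 7 calendar put the repeat scans before a standard-of-care biopsy for residual disease. That biopsy is not dated.

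**The concern.** The dependent variable of the primary response analysis has neither a date nor a definition. Two analysts with the same charts could build different outcome variables, and the choice could be made after the scans have been read.

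If T6 is simply month 6, the predictor (the T0 to T1 change) is completed at the same time as the outcome. The regression and the McNemar tests would then describe how well the scans classify a patient's status at that visit, while the hypothesis would have them reported as prediction.

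The reference standard adds a second problem. Imaging is one of its components, and nothing excludes the PET and MRI under comparison. Section 5.3 has the study team send scan results to the treating physicians, so those results can shape the clinical follow-up that defines response. Whichever modality entered the label would be favoured in a comparison whose purpose is to rank PET against MRI.

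**Working it through.** The plan states no figure for this point. The check sets the time labels and reference statements side by side.

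**1. Time points that exist.**
- Section 10.2 defines T0 as baseline and T1 as six months after the start of treatment. T2 to T5 do not appear.
- The section 7 calendar has columns for pre-study, scan date, 24 to 72 hours post-scan, and 12 months. None is called T6.
- T6 occurs only in the two primary analyses of section 10.2.

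**2. Candidate readings of T6.**
- *Month 6.* The lag from T1 is 6 − 6 = 0 months. Six months is the recurring post-treatment time in the plan (section 1, section 2.5, section 5.2, section 7, section 10.2).
- *Six months after T1.* This would be month 6 + 6 = 12. No response assessment is scheduled then; the 12-month calendar column is chart review.
- *A sixth assessment.* No such series is defined.
- *A label left over from another protocol.* The secondary analysis describes PFS as the length of a drug response, although the treatment is brachytherapy, so reused text is possible. The label would then have no meaning here.
- *Month 24.* This fits poorly. The power paragraph has responders who later progress by two years, so response is assigned before then.

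Month 6 is the most natural reading, and it gives zero lag. Under the others, no defined assessment supplies the outcome.

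**3. Whether chart review could supply a later outcome.** Section 6.3 follows charts for 12 months post-scan. The section 7 footnote says 24 months from the initial scan. If the section 6.3 clock starts at the post-therapy scan (an assumption), it ends about 6 + 12 = 18 months after treatment, short of the 24-month PFS target. The two statements must be reconciled before any later response date, or PFS at 24 months, can be relied on.

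**4. Components of the reference.**
- PSA: a poor efficacy measure after HDR by the protocol's own account, yet part of the response standard with no stated weight.
- Imaging: study PET/MRI is not excluded.
- Tissue: the component least dependent on the images, but from a biopsy with no date or window.

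**5. Illustrative bound only.** Suppose the label rested on PSA alone, with the Phoenix sensitivity of 65% and specificity of 77% (section 2.1), 25 non-responders and 75 responders (section 10.2), and non-response as the positive class.
- Labelled non-responder: 0.65 × 25 + 0.23 × 75 = 16.25 + 17.25 = 33.5.
- Apparent sensitivity of a perfect scan: 16.25 / 33.5 = 48.5%.
- Labelled responder: 0.77 × 75 + 0.35 × 25 = 57.75 + 8.75 = 66.5.
- Apparent specificity of a perfect scan: 57.75 / 66.5 = 86.8%.
- With 20 non-responders the pair is 41.4% and 89.8%; with 30 it is 54.8% and 83.7%.
- With response as the positive class, sensitivity and specificity swap.

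This shows that a poor reference can cap the apparent accuracy of any scan. It is not an estimate for this trial, whose stated reference is a composite.

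**The case against.** The strongest reply is that the defect is one undefined label. Since T0 and T1 look like visit indices and month 6 is already called T1, T6 need not mean month 6. This stands in part: a reader might infer that T6 can only be month 6, and the documents do not go that far. But no alternative rescues the analysis, because none has an assessment behind it.

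A reader might also infer that the protocol declares PSA unable to show response. It does not. Section 2.1 calls PSA a poor measure and says early false negatives may occur; it makes no statement about month 6. Nor can the label be called mainly PSA-driven: section 10.2 lists imaging and tissue as well, a biopsy is expected after the repeat scans, and Phoenix is not named as the response criterion.

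The illustrative accuracy figures are open to the same reply. They assume a PSA-only label, apply figures quoted for clinical recurrence to an early response label, and depend on an unstated choice of positive class.

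Finally, the effect is limited in scope. The PFS hypothesis does not use T6, and the outcomes in section 10.3 are counts of assessable participants. All of this is fair. It narrows the point to the primary response analysis of section 10.2, where the defect remains.

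**Conclusion.** The point holds for the two primary response analyses of Aim 2. T6 is undefined, and response has no date or criteria, so those analyses cannot be run as written. If T6 is month 6, which is an inference though the most natural one, the lag is zero and the claim of prediction is not tested. Separately, the wording of the reference standard lets the study PET/MRI contribute to the label it is judged against.

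The documents do not allow the bias to be sized, because they do not say how often tissue, imaging or PSA decides the label. The 48.5% and 86.8% figures are a worst-case illustration and should not be cited as the expected effect. The 24-month PFS question is not affected by T6, but it does depend on settling the chart-review period. The outcome should be defined before any patient is classified as a responder or non-responder.

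**What to change.** In section 10.2:

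1. Replace T6 with a named, dated outcome.
2. For a month-6 outcome, define response by histology (residual cancer yes or no) from the standard-of-care biopsy that sections 2.5 and 7 place after the repeat scans, with a stated window for its date.
3. Exclude study PET and study MRI from the response label, and do not let month-6 PSA alone assign it.
4. Describe the result as detection of residual disease at about six months, and leave prediction to 24-month PFS.
5. Report how many patients have no biopsy. Keep them in a sensitivity analysis that uses later clinical follow-up without study imaging, to show any selective verification. This matters because section 6.3 has investigators help choose biopsy sites from the PET/MRI findings.
6. Reconcile the 12-month chart review in section 6.3 with the 24 months in the section 7 footnote.

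The change needs no new visit or procedure. Its costs are fewer patients in the primary response analysis, hence less than the roughly 75 and 25 assumed for power if biopsies are missed, and a narrower claim. No biopsy completion rate is given, so the size of that loss is unknown.

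### Section 10.2 tests PFS on a change known only at the 6-month scan, with no clock start or landmark, an inconsistent population, and a power claim that the expected responder events do not support

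*Combined protocol and SAP*

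**What the plan says.** Section 10.2 takes its population from Aim 1: "Participants: Those enrolled in Aim 1". The predictor is the change in uptake or MRI features between baseline (T0) and a scan six months after treatment starts (T1). The PFS analyses, labelled secondary within Aim 2, are "log-rank tests of PFS time (length of drug response) on patients dichotomized as above/below the median change in PET/MRI measures" and "Cox proportional-hazards regressions of PFS on amount of T1-T0 change in PET/MRI measures". Neither is limited to a subset, and neither says when PFS time begins.

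The power text uses a different group: "Median-change groups of ~40 each among the responders will provide 90% power at one-sided 5% error". The effect it is sized for is a hazard ratio of 2.5. Its planning rates are "We expect a 70-80% response rate to treatment, and 20% of responders progressing by two years", and the response analysis is sized on "A sample size of ~75 responders and ~25 non-responders".

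Four related points bear on timing:
- Section 10.2 gives response and PFS the same reference standard (PSA, imaging and tissue from routine follow-up) and places response at a time T6 that is never defined.
- Section 2.5 and the Section 7 calendar put the residual-disease biopsy after the 6-month scans.
- Section 1 states the aim as forecasting 24-month PFS from the 6-month imaging.
- Chart review lasts 24 months from the initial scan in footnote b of Section 7, but 12 months after the scan in Section 6.3.

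**The concern.** A covariate measured at month 6 cannot predict an event at month 4. If the clock starts at baseline or at treatment, and the T0-T1 change enters as a fixed covariate, a patient who failed before T1 but was still scanned is classified by a measurement made after the failure. A patient who failed and was not scanned drops out, so those who are analysed have been selected on having reached T1. Neither case supports the forward-looking claim in Section 1.

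The population matters because response and PFS share a reference standard. If patients judged to have failed at about T1 also count as PFS events, the PFS hazard ratio partly repeats the response analysis. The scan may also help to generate the event. Under Section 5.3 the results go to the treating physicians, and under Section 6.3 the investigators help choose lesions for biopsy from the PET/MRI findings.

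Two statisticians could follow Section 10.2 faithfully, analyse different patients with different clocks, and report different hazard ratios.

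**Working it through.** **Inputs, all from Section 10.2.** Response rate 70-80% of 100 patients; 20% of responders progress by two years; about 75 responders and 25 non-responders; median-split groups of about 40 (so about 80 responders); hazard ratio 2.5; one-sided 5%; 90% power; 1:1 split.

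**Step 1. Events needed for the stated power.** Schoenfeld: d = 4(z₀.₉₅ + z₀.₉₀)² / (ln HR)² = 4(1.645 + 1.282)² / (0.916)² ≈ 41. Freedman's formula gives 47.

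**Step 2. Events the plan's rates supply among responders.** 0.20 × 75 = 15 and 0.20 × 80 = 16 (14 if only 70 respond). Power = Φ(√d × ln HR / 2 − 1.645):
- d = 15: Φ(1.774 − 1.645) = 55%
- d = 16: Φ(1.833 − 1.645) = 57%

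Freedman gives 51-53%. The stated 90% is not reproduced in responders. With 15-16 events, 90% power requires a hazard ratio of about 4.3-4.5.

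**Step 3. What would reproduce 90%.** Adding the 25 non-responders as events gives 25 + 15 = 40, and power Φ(2.898 − 1.645) = 89.5%.

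**Step 4. Share of events at about T1 if non-responders are analysed, count as events and are all dated at about T1.**
- 70% response: 30 / (30 + 14) = 30/44 = 68%
- 75% response: 25 / (25 + 15) = 25/40 = 62.5%
- 80% response: 20 / (20 + 16) = 20/36 = 56%

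At 75% response, this share exceeds half only if more than 80% of non-responders are dated at about T1 when the rest become later events (20/40 is exactly half), or more than 60% when the rest never become events (15/30 is exactly half).

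**Step 5. Share of events before month 6 if only responders are analysed.** Assume a constant hazard and two years counted from the start of treatment; the documents state neither. The proportion of responders progressing by month 6 is 1 − 0.8^(6/24) = 5.4%. That is 4.1 of 15 events (75 responders) or 4.3 of 16 (80 responders), about 27%. If a responder is by definition event-free at month 6, the share is zero.

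**Step 6. Power after a 6-month landmark in responders, same assumptions.** 15 − 4.1 = 10.9 events give about 45%; 16 − 4.3 = 11.7 events give about 47%. If all 15-16 events fall after the landmark, the 55-57% of Step 2 applies.

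**The case against.** A reader might infer that PFS is tested on every enrolled patient and that most events precede or coincide with the scan said to predict them. The documents do not establish either.

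On population, the power text places the groups among responders, and the gloss on PFS time as the length of response describes something only responders have. Against that, the Aim 2 population and the analysis sentence are unrestricted, and the 90% figure is recovered only with about 40 events. That match is suggestive, but it does not prove that the authors counted non-responders. The text is inconsistent, and neither reading can be taken as settled.

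On timing, the 56-68% needs three conditions that the plan does not state: non-responders are analysed, they count as PFS events, and those events are dated at about T1. T6 is undefined and could fall later than T1. Failures found at the residual-disease biopsy come after the scan, though soon after. Section 2.1 notes that PSA failure may be missed early because regrowth takes time, which argues against many PSA-defined events before month 6.

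It is also fair to say that PET and MRI changes cover the same interval. The timing problem affects both, and nothing shows that it favours PET. That non-responders have high uptake at T1 is what Aim 2 sets out to test, not a given. The test is labelled secondary within Aim 2, and the outcomes in Section 10.3 are counts of assessable participants, although predicting 24-month PFS is part of a primary objective in Section 2.5.

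These points limit the size of the problem. They do not supply the missing time origin, landmark or population.

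**Conclusion.** The concern holds as a defect of specification with a numerical consequence. As written, events at or before T1 can be counted as predicted by a later measurement, because Section 10.2 sets no clock start or event-free condition and names two populations.

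The size depends on the reading. The 56-68% share applies only under the three conditions above and should be cited only as that scenario. Among responders the early share is a minority, about 27% under a constant hazard, and possibly none.

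The power shortfall is firmer. On the plan's own rates the responder comparison has 15-16 events against about 41 needed, so power is about 55-57% rather than 90%, and about 45-47% once a 6-month landmark is applied under a constant hazard. Either reading leaves a problem: with non-responders counted, the events overlap with the response analysis; with responders only, the power claim fails.

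**What to change.** In Section 10.2:
- Define a PFS event, start the clock at the T1 assessment, and include only patients event-free at that point. Use this population in both the analysis and the power text.
- State how failures found at the residual-disease biopsy just after the scan are classified. Counting them as PFS events would bring the response endpoint back into the PFS test.
- Follow to 24 months from the initial scan, the chart-review period in Section 7, and reconcile this with the 12 months in Section 6.3. A horizon of 24 months from T1 would need longer follow-up than either.
- Apply the same landmark and patient set to the log-rank and Cox analyses, for PET and MRI alike.
- Keep early failures in the response analysis, and define T6.
- Restate the power from the expected post-landmark events, with the assumed timing shown.

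This is a change of wording and needs no new data, provided that the 24-month chart review is the one carried out. The cost is fewer events in the PFS test and a much lower stated power for a secondary comparison.

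### Aim 2 names no lead PFS analysis and powers only the median split, where the plan's own rates give about 15-16 events and about 51-57% power, not 90%

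*Combined protocol and SAP*

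**What the plan says.** Section 10.2, Statistical Analysis, gives two secondary analyses of PFS. Item (a) is "log-rank tests of PFS time (length of drug response) on patients dichotomized as above/below the median change in PET/MRI measures". Item (b) is "Cox proportional-hazards regressions of PFS on amount of T1-T0 change in PET/MRI measures". Nothing says which of them decides the PFS hypothesis, namely that change in tracer uptake predicts PFS better than MRI does.

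The power paragraph of the same section covers only item (a): "Median-change groups of ~40 each among the responders will provide 90% power at one-sided 5% error", for "differences in PFS hazard ratios as small as 2.5". It gives no event count and no power for item (b). Its planning rates are "We expect a 70-80% response rate to treatment, and 20% of responders progressing by two years", and it works with "A sample size of ~75 responders and ~25 non-responders".

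Section 10.2 calls the PFS hypothesis secondary. Prediction of PFS at 24 months is nevertheless part of a primary objective in the Synopsis and in section 2.5.

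**The concern.** There are two linked faults.

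First, the power of a log-rank test depends on the number of events, not the number of patients. The plan sizes the comparison by group size, and its own progression rate implies few events.

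Second, the only powered analysis cuts a measured change at the sample median, while the analysis that keeps the change whole has neither priority nor a power statement. With so few events the two can easily disagree. In a simulation of 75 responders with 15 events and a log-linear effect, one was significant and the other not in about 29% of trials. With no lead analysis named, the choice could be made after the results are seen.

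At stake is a conclusion tied to a primary objective. A non-significant log-rank result would be read against a 90% power claim that the plan's rates do not support.

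**Working it through.** **Inputs (all from section 10.2).** About 75 responders; 20% of responders progressing by two years; two median-change groups of about 40, so about 80 in all; hazard ratio 2.5; one-sided 5%; stated power 90%.

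**Events (derived).** 75 × 0.20 = 15 and 80 × 0.20 = 16. At the low end of the response range, 70 × 0.20 = 14.

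**The plan's figure for the split.** Schoenfeld, equal groups: power = Φ(√d × ln HR / 2 − 1.645), with ln 2.5 = 0.916. Freedman: power = Φ(√d × (HR − 1)/(HR + 1) − 1.645).

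| Events d | Schoenfeld | Freedman |
|---|---|---|
| 14 | 52.8% | 48.4% |
| 15 | 55.2% | 50.6% |
| 16 | 57.4% | 52.8% |
| 40 | 89.5% | 85.7% |
| 41 | 90.1% | 86.4% |

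At 15 events Schoenfeld is Φ(3.873 × 0.458 − 1.645) = Φ(0.13) = 55%. The 90% is not reproduced at the planned rates. It would need about 40 events in total, which the documents do not project.

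As a cross-check, take 40 per group with constant hazards in ratio 2.5 and an average of 20% progressing. The two-year proportions are then 12.2% and 27.8%, and a two-proportion test has 54% power.

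**What 90% would need.** Schoenfeld: 4 × (1.645 + 1.282)² / 0.916² ≈ 41 events. Freedman: 47. At a 20% event rate, 41 / 0.20 = 205 responders. With 15 events, the hazard ratio detectable with 90% power is exp(2 × 2.926 / √15) ≈ 4.5.

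**Cost of the median split.** For a normal predictor with a modest log-linear effect, a median split has efficiency 2/π = 64%, a loss of about 36%. To put the Cox model on the same footing, let the two halves differ on average by a hazard ratio of 2.5. The halves of a normal variable differ in mean by 2 × √(2/π) = 1.596 SD, so the log hazard ratio per SD is 0.916 / 1.596 = 0.574, a hazard ratio of 1.78 per SD. Power is then Φ(√d × 0.574 − 1.645):

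- 14 events: 69%
- 15 events: 72%
- 16 events: 74%
- 90% power: (2.926 / 0.574)² ≈ 26 events

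**Simulation (75 responders, about 15 events, one-sided 5%).** The distribution of the change and the shape of its effect are assumptions, because the documents give neither.

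| Assumed shape | Split | Continuous Cox |
|---|---|---|
| Normal change, log-linear effect | 46-52% | 69-71% |
| Right-skewed change, effect linear in its log | 46% | 66% |
| Step of hazard ratio 2.5 at the median, normal change | 42-53% | 38-39% |
| Long tail on the low-risk side, effect linear in its log | 46-47% | 38-39% |

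In the first row, the 46% comes from runs stopped at exactly 15 events and the 52% from runs in which the count varies around 15. The skewed rows use the raw, untransformed change in the Cox model.

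**The case against.** The strongest reply is that item (b) already analyses the undivided amount of change. A reader might infer that the PFS analysis rests on a median split and that the plan throws away about a third of its information. The documents do not support that: the Cox model is planned, and being listed second does not make it subordinate. What stands is narrower: no lead analysis is named and only the split is powered.

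A second reply is that the gain from a continuous analysis is not assured. This stands. The 64% and the 70-72% need a roughly normal change and a log-linear effect, and two of the four simulated shapes reverse the order. The measures also include MRI features, which may be ordinal, so a hazard ratio per SD need not suit every model.

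A third reply is that the event shortage is the real defect. This also stands. A reader might infer that dropping the split restores the claimed power. It does not: at 14-16 events the Cox model reaches 69-74% under favourable assumptions.

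Finally, the count of 15-16 is for responders, as in the power statement, whereas item (a) refers to patients. Including the roughly 25 non-responders would add events at a rate the documents do not give.

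**Conclusion.** The point holds in this form: section 10.2 leaves the lead PFS analysis open, powers only the split, and claims 90% where its own rates give about 51-57% at 15-16 events. That shortfall needs no assumption about the shape of the effect beyond proportional hazards. It does depend on 20% of 75-80 responders progressing and being observed to two years. Section 6.3 gives 12 months of chart review after the scan and footnote b of the Study Calendar gives 24 months from the initial scan. These must be reconciled, since the shorter period would yield fewer events.

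The information loss from the split, about 36%, and the gain to about 70-72% power with continuous Cox are conditional on a roughly normal change and a log-linear effect. They support preferring the Cox model but do not guarantee a gain. The change is worth making, though the hypothesis is labelled secondary and the better analysis is already listed.

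**What to change.** In section 10.2:

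1. Name the Cox model on continuous change, suitably transformed if skewed, as the lead PFS analysis, fitted for each PET tracer and for MRI. State also how the tracers will be compared with MRI, since separate models do not by themselves test which predicts better.
2. Keep the median split for Kaplan-Meier display.
3. State the analysis population (responders or all patients) and the expected number of events.
4. Replace the 90% statement with power at about 15 events, one-sided 5%: about 51-57% for the split at hazard ratio 2.5, and about 70% for Cox at hazard ratio 1.78 per SD, with the normal and log-linear assumptions stated. Add that the hazard ratio detectable by the split with 90% power is about 4.5.

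The cost is wording only: no added patients, scans or analyses. The downside is a less favourable power statement and reliance on a log-linear effect, which about 15 events can check only weakly.
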